4.1 Study population

Inclusion Criteria

Older HIV-positive cohort (n=1000):

- documented HIV infection
- age ≥ 50 years at study entry
- self defined white or black African ethnicity
- likely route of HIV acquisition via sexual exposure
 - Either by male to male exposure if white or by heterosexual exposure if white or black African
- able to comprehend study patient information leaflet

Subjects with primary HIV infection are eligible and investigators are encouraged to recruit such subjects.

Our target population (those of white or black African ethnicity and those infected with HIV via sexual routes) has been chosen as these groups represent the vast majority of older HIV-positive individuals attending for care in the UK; analyses of other groups (e.g. injection drug users, those infected through blood/blood products and transgender individuals), who may have very different needs and outcomes, would likely be under-powered.

Younger HIV-positive cohort (n=500):

- documented HIV infection
- age < 50 at study entry*
- self defined white or black African ethnicity
- likely route of HIV acquisition via sexual exposure
 - Either by male to male exposure if white or by heterosexual exposure if white or black African.
- able to comprehend study patient information leaflet

* this group will comprise of at least 150 subjects in each of the following age groups: 20-29, 30-39, 40-49 years. Recruitment will be monitored by the Study Monitoring Team

HIV-negative cohort (n=500):

- documented negative HIV test at screening
- age ≥ 50 years at study entry
- self defined white or black African ethnicity
- registered with a General Practitioner and gives permission for contact with that GP.

Exclusion Criteria

- in the opinion of the investigator, those unable or unwilling to comply with the requirements of the study
- life expectancy less than 6 months

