4.3 Study Objectives

Clinical manifestations

- To describe the incidence and presenting features of serious medical conditions (such as cardiovascular, liver, renal disease, cancer and fragility fractures) in the three cohorts.
- To describe the outcomes of serious medical conditions (including time to recovery/resolution, where applicable, the incidence of complications and use of health-care).
- To compare NC function in the three cohorts, and to identify predictors of NC function.
- To compare the levels of musculoskeletal pain in the three cohorts, to identify predictors of this and to describe the health-care needs of those affected.
- Among women, to assess the effects of menopausal status on cardiovascular disease, BMD and lipid/glucose metabolism.

Antiretroviral pharmacokinetics and drug interactions

- To describe plasma (or, where appropriate, intracellular) concentrations of antiretroviral agents (tenofovir, non-nucleoside reverse transcriptase, protease, integrase and entry inhibitors) at baseline in the older HIV-positive cohort, and to compare these to those seen in younger HIV-positive patients.
- To describe the incidence of toxicities/drug discontinuations and immunological/virological responses to cART in the HIV-positive cohorts and to assess correlations between these events and plasma drug concentrations.
- To describe the level of poly-pharmacy in the older HIV-positive cohort and thus the potential for/prevalence of unwanted drug-drug interactions.
- To determine whether accumulation of renally-excreted antiretroviral drugs (e.g. tenofovir) increases their potential to cause renal injury in older HIV-positive people.

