6.0 Study Specific Procedures

6.1 DEXA scanning

All study subjects will undergo a regional (hip and spine) and whole body DXA scan where available (only if urinary β hcg is negative in female subjects under the age of 50). Total and regional bone mineral density Z and T scores will be estimated and total and regional fat and lean mass calculated. All scans will be performed by medical staff and reported by a consultant radiologist and should be performed within 30 days of the clinic visit.

The reports of the scans will be sent to the patients GPs where permission for contact is in place. In the cases where no permission is granted for GP contact, the results will be sent to the health care professional in charge of that patient within the clinic. In all cases any abnormalities detected will therefore be actioned.

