8.0 Statistical Considerations

8.1 Methods and planned analysis clinical manifestations

Detailed information on clinical events will be collected at baseline and at each visit. As we currently have very little data on the incidence, presenting features or outcomes of these events in older HIV-positive individuals, many of the analyses will be descriptive. We will describe the proportion of individuals in the three cohorts who have already experienced each event at baseline (prevalence) and the proportions who develop a new (or recurrent) event over follow-up (incidence). Confidence intervals will be generated for these proportions. Statistical comparisons of the prevalence/incidence of each event (where numbers are sufficiently large) will be performed using logistic/Poisson regression.

Sample size and power

The sample sizes for baseline analyses will be 1000, 500 and 500 respectively.

Based on data from Goulet *et al*⁵, we expect baseline prevalence rates of liver/renal disease of around 14.0%/4.6% among those aged >50 years versus 5%/1% in younger HIV-positive patients and 3.1%/2.3% in HIV-negative patients. Our study will have 70-100% power to detect similarly-sized differences between the three cohorts. Serious medical conditions are, however, expected to be rare, even in the older groups. For example, based on the limited data that exist (from various sources), we may see at most only 17, 20, and 7 cases of myocardial infarction, malignancy and liver failure, respectively, in the HIV-positive groups combined; analyses of incidence of these events will therefore be descriptive. Incident fractures and chronic kidney disease may be more common (105 and 100, respectively), but these numbers will still limit multivariable analyses. NC function impairment and current pain are expected to be present in 40% (n=540) and 63% (n=850) of the HIV-positive subjects at baseline; we will therefore have >95% power (5% significance level) to detect differences of 10% between the proportions with each event in the older HIV-positive and other cohorts; these sample sizes will also permit multivariable analyses of predictive factors. Among the older women (130 or so in the white/black African groups combined), we estimate that 70 (54%) will have already experienced the menopause at baseline; our analyses will be limited to simple comparisons of biomarkers in the two groups.

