8.3 Analysis plan

Cross-sectional analyses of clinical manifestations and therapeutic drug concentrations, and their association with patient factors, will be undertaken at the start of the project once baseline visits are complete; analyses of associations with outcomes will be performed in the following years.

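### Section 8.1 limits the menopause biomarker analysis to simple comparisons with no stated age adjustment, so age differences could be read as menopausal effects

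*Combined protocol and SAP*

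**What the plan says.** The objective in section 4.3 reads "Among women, to assess the effects of menopausal status on cardiovascular disease, BMD and lipid/glucose metabolism". Entry to the older HIV-positive and HIV-negative cohorts requires "age ≥ 50 years at study entry" (section 4.1), with no upper limit.

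The only method specific to the biomarker part of this objective is in the sample-size paragraph of section 8.1. It begins "Among the older women (130 or so in the white/black African groups combined", estimates that 70 (54%) of these women will be past the menopause at baseline, and concludes that "our analyses will be limited to simple comparisons of biomarkers in the two groups". Just before this, for neurocognitive impairment and pain, the same paragraph says "these sample sizes will also permit multivariable analyses of predictive factors".

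Three other statements bear on the point:

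- Section 8.1, on clinical events: "Statistical comparisons of the prevalence/incidence of each event (where numbers are sufficiently large) will be performed using logistic/Poisson regression".
- Section 6.1, on bone density: "Total and regional bone mineral density Z and T scores will be estimated".
- Section 8.3, in general terms: "Cross-sectional analyses of clinical manifestations and therapeutic drug concentrations, and their association with patient factors". It names neither age nor the menopause comparison.

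**The concern.** Menopausal status is closely tied to age; the questionnaire in Appendix 1 (Q87) itself tells participants that periods normally cease in the forties or fifties. Among women recruited from 50 upwards, those not yet past the menopause will tend to sit near the lower age limit, while post-menopausal women can be any age above it. A plain two-group comparison therefore contrasts older with younger women as well as menopausal states.

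Where a biomarker changes with age, the comparison cannot say which of the two produced a difference, yet the objective asks about menopause. Lipids and glucose are clearly exposed. BMD is exposed unless the age-referenced Z score is the outcome, and section 8.1 does not say which score will be used.

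The cardiovascular-event part of the objective is left out of this point, because section 8.1 assigns event comparisons to regression where numbers allow.

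**Working it through.** **The plan's own figure.** 70/130 = 53.8%, which reproduces the stated 54% and leaves about 60 women in the other group. No effect size, SD or power is stated for this comparison, so there is no power figure to reproduce.

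**Is age handled anywhere?** The multivariable remarks in 8.1 concern neurocognitive impairment, pain, fractures and kidney disease. Section 8.2 controls confounders only in the virological-failure model. Section 8.3 is generic. That the simple comparisons are unadjusted is an inference, but the natural one, since the text sets them apart from the analyses that can be multivariable.

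**How large could the error be?** The documents give no age distribution for these women and no biomarker-age correlation. The following inputs are all assumed:

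- mean age gap g between the groups: 3, 5 or 8 years
- within-group age SD s: 4, 5 or 6 years
- biomarker-age correlation ρ: 0.1, 0.2 or 0.3
- no true menopausal effect, and a linear age effect

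This gives 27 scenarios. The biomarker is in SD units.

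Formulas, with p = 70/130, p(1−p) = 0.2485 and √0.2485 = 0.4985:

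- Total age SD: T = √(s² + 0.2485 g²)
- Correlation of age with menopausal status: r = 0.4985 g/T
- Bias of the unadjusted difference: ρg/T
- SE unadjusted: √[(1 − ρ²r²)(1/70 + 1/60)]
- SE adjusted: √[(1 − ρ²)/(1 − r²) × (1/70 + 1/60)]
- RMSE: √(bias² + SE²)

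Central case (g = 5, s = 5, ρ = 0.2): T = √(25 + 6.21) = 5.59; r = 2.49/5.59 = 0.446; bias = 0.2 × 5/5.59 = 0.179.

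| g, s, ρ | r | Bias, unadjusted | SE unadjusted | SE adjusted | RMSE unadjusted | RMSE adjusted |
|---|---|---|---|---|---|---|
| 3, 6, 0.1 | 0.242 | 0.049 | 0.176 | 0.180 | 0.182 | 0.180 |
| 5, 5, 0.2 | 0.446 | 0.179 | 0.175 | 0.193 | 0.250 | 0.193 |
| 8, 4, 0.3 | 0.706 | 0.425 | 0.172 | 0.237 | 0.458 | 0.237 |
| 8, 4, 0.1 | 0.706 | 0.142 | 0.175 | 0.247 | 0.226 | 0.247 |

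Bias runs from 0.05 to 0.14 SD at ρ = 0.1, 0.10 to 0.28 at ρ = 0.2, and 0.15 to 0.42 at ρ = 0.3. With no menopausal effect, a nominal 5% unadjusted test would reject in about 6% to 70% of studies, and in about 17% in the central case. Simulation of the first three rows (20,000 runs each) gave unadjusted bias of 0.050, 0.178 and 0.425, and adjusted bias of 0.00.

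A second parameterisation, with assumed gaps of 3 to 7 years and biomarker slopes of 0.02 to 0.06 SD per year, gives a similar range: bias = gap × slope = 0.06 to 0.42 SD.

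**What adjustment costs.** The SE ratio (adjusted to unadjusted) is 0.99 to 1.41. The difference detectable with 80% power (2.8 × SE) is about 0.49 SD unadjusted and 0.49 to 0.70 SD adjusted; the upper end is 0.493 × √1.99, taking variance inflation alone. Power for 0.5 SD is 81–82% unadjusted and 52–82% adjusted.

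**Net.** The adjusted estimate has the smaller RMSE in 23 of 27 scenarios. The four exceptions all have ρ = 0.1: (g, s) = (5, 4), (8, 4), (8, 5) and (8, 6).

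**The case against.** The plan is open about the limit. It ties it to small numbers, says many analyses will be descriptive, and nowhere in 8.1 promises to attribute a difference to menopause. The sentence sits in sample-size text that the synopsis presents as exemplar calculations, so it need not be a full model specification. Simple need not mean unadjusted, and 8.1 does not define its biomarkers. Planned Z scores may already deal with age for BMD. All of this stands and keeps the point minor, but none of it supplies a stated age adjustment. Small numbers argue against a large predictor model; they do not rule out one continuous age term for a continuous biomarker in 130 women.

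The magnitude has no anchor in the documents, and at a correlation of 0.1 the bias is below one standard error. That also stands, so the ranges are illustration only.

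The strongest technical objection is that the grid assumes equal age spread and a correct linear age term, whereas the groups may overlap poorly. A further check with right-skewed ages starting at 50 and unequal spread (assumed correlation 0.2, linear age effect) still favoured adjustment, with RMSE about 0.18–0.19 against 0.21–0.25. This answers the equal-spread point. It does not remove the reliance on extrapolation and linearity where overlap is poor.

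Finally, the event-regression sentence follows text on the three cohorts and does not mention menopause, so leaving cardiovascular events aside is a concession to the plan and not evidence that they are covered.

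**Conclusion.** The concern holds. As written, the comparison does not separate menopause from age, so it answers the biomarker part of the objective only partly. This rests on reading the simple comparisons as unadjusted, which is an inference from the context.

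The size of the error is unknown. About 0.05 to 0.42 SD is an illustration under wholly assumed inputs, with 0.18 SD in the central case, and it applies to BMD only if Z scores are not the outcome. The consequence is confined to one of nine objectives, and the plan itself calls the analysis limited. It is a change to consider, held with medium confidence.

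**What to change.** In section 8.1, state that:

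- each biomarker will be compared by linear regression on menopausal status, adjusted for continuous age and for ethnicity (the two ethnic groups are pooled), and for HIV status if HIV-negative women are included, with a 95% confidence interval;
- for BMD, the score used is named; the Z score of section 6.1 may serve as the age-referenced outcome;
- the age distribution and its overlap will be shown by menopausal status;
- the unadjusted comparison is kept as descriptive, and results are described as associations.

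If the sponsor prefers not to adjust, labelling the comparison descriptive, showing ages by group and not attributing differences to menopause would meet the main risk, but would leave the biomarker part of the objective only partly answered.

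The cost is two or three sentences. Age and ethnic group are already collected at baseline (section 5.2). The statistical price is the loss of precision shown above, up to 41% on the standard error under the assumed range. Where age overlap is poor, the adjusted estimate must be reported with the caution that it relies on extrapolation and a linear age term.

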8.2 Methods and planned analysis for pharmacokinetic analyses

Plasma drug concentrations from the older HIV-positive cohort will be compared with suggested minimally effective concentrations of each drug and to data from a large sample of historical HIV-positive controls obtained from a large therapeutic drug monitoring database held by the University of Liverpool. As plasma drug concentrations have a skewed distribution, non-parametric methods (e.g. Mann-Whitney tests) will be used. Proportional hazards regression will be used to investigate the impact of drug concentrations on time to virological failure (defined as two consecutive viral loads >50 copies/ml whilst remaining on treatment) after controlling for other confounders and adherence. All co-medications and drug doses, regardless of the prescriber, will be documented and the potential for drug-drug interactions investigated. Drug interactions will be defined as clinically significant (severe – drugs should not be co administered / potential interaction where dose adjustment may be necessary) or minor, and associations determined with any side effects reported.

Sample size

Based on current treatment guidelines, we anticipate that around 90% of older HIV-positive participants (n=810) will be receiving cART, with 60% of these patients (n=486) receiving tenofovir. These sample sizes are in excess of those generally used for other published studies of antiretroviral pharmacokinetics, providing further scope for multivariable analyses

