5.2 Visit 1 (Baseline visit)

The baseline visit will perform evaluations as per schedule of visits (2.0).

The baseline visit is expected to take 1-2 hours; if possible the subject should attend fasted. The following information will be collected:

- Baseline demographics: age; sex; ethnic group; sexual orientation; country of birth; education.
- Socio-economic status: immigration status; employment; household dependents; household income; housing.
- Quality of life questionnaire.

- Anthropometrics: height; weight; body mass index; waist circumference.
- Lifestyle factors: current/past cigarette smoking; alcohol use; recreational drug use.
- Full clinical history: to include cardiovascular events (hypertension, myocardial infarction, angina or acute coronary syndromes, cardiogenic arrhythmias, coronary artery stenting/bypass grafting, peripheral vascular disease), renal failure, liver failure, diabetes, malignancies, falls, fractures, joint disease or joint replacements.
- Measurement of hand grip strength using an automated device.
- Simple measurement of walking speed over a distance of 15 feet (457 cms).
- Blood pressure will be estimated using an automated device.
- Menstrual and reproductive history (women), including menopausal status
- Family medical history: to include any cardiovascular disease, type 2 diabetes mellitus, malignancies, mental illness, dementia or Alzheimer's disease, parental hip fractures.
- Current and recent (over past 12 months) antiretroviral use: type of antiretroviral; start/stop dates; dose; frequency of dosing; side effects; reasons for prior changes/discontinuations.
- Duration of HIV infection and date of HIV-seroconversion if known
- Adherence assessment (see study questionnaire in appendix 1)
- Use of any other medications (including, but not limited to, anti-hypertensives, anti-depressants, vitamin D and/or calcium replacement therapy, lipid-lowering drugs, regular use of analgesics, herbal remedies, other over-the-counter drugs): type of drug; start/stop dates; dose; frequency of dosing; side effects.
- Neurocognitive function: specific memory and cognitive testing assessing cortical and sub-cortical function.
- Pain assessment: regional and widespread pain collected using a validated mannequin; nature of onset; duration; intensity; resulting disability (see study questionnaire in appendix 1)

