6.2 Blood sampling

Pharmacokinetic sampling

Prior to blood taking for pharmacokinetic sampling, time of food intake nearest last dose prior to sampling and food content will be recorded (fasting, light snack, heavy meal). Time of last dose and time of sampling will be recorded.

Efforts will allow for blood sample collection at least 5 hours after the drug dose is administered in order to ensure the sample is post-absorption and to enable the modeling of sparse data.

Blood sample (4-5 mL in EDTA or lithium heparin) collections for the determination of the plasma concentrations of tenofovir and the third agent (i.e. a non-nucleoside reverse transcriptase, protease, entry or integrase inhibitor) in the patient's regimen will be drawn at steady-state. Samples will be processed to isolate plasma and stored at -20°C until shipment to the central laboratory at the University of Liverpool for analysis.

Blood for storage

Blood (serum and plasma,) and urine samples will be collected at visits 1 and 3 stored for subsequent projects of the potential pathogenic mechanisms underlying age-related diseases. This will include assessment of vitamin-D and PTH and probably DNA analysis. Approximately 20mls of blood will be taken. These samples will be stored in a designated central repository for the POPPY study. The analyses will be instigated only by the steering

committee of this trial and will not be for general Biobank access. Specific permission will be sought from all participants for this storage and also for any DNA analysis.

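### Section 8.2 analyses drug concentrations without using time after dose, although samples may be drawn at any time from about 5 hours and the times are recorded

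*Combined protocol and SAP*

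**What the plan says.** On sampling, section 6.2 says: "Efforts will allow for blood sample collection at least 5 hours after the drug dose is administered". This is an aim rather than a requirement. It has no upper limit and does not ask for a sample at the end of the dosing interval. The reason given is "to ensure the sample is post-absorption and to enable the modeling of sparse data". Samples "will be drawn at steady-state", and "Time of last dose and time of sampling will be recorded". For each antiretroviral, section 5.2 collects "type of antiretroviral; start/stop dates; dose; frequency of dosing". Time after dose and dosing interval can therefore be worked out for each sample whose times were recorded.

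On analysis, section 8.2 says: "Plasma drug concentrations from the older HIV-positive cohort will be compared with suggested minimally effective concentrations of each drug". The older cohort is also compared with historical controls from a therapeutic drug monitoring database. Because concentrations are skewed, "non-parametric methods (e.g. Mann-Whitney tests) will be used". Drug concentration then enters a proportional hazards model for virological failure, controlling for adherence and for confounders that are not listed. Section 8.2 mentions neither time after dose nor a sparse-data model, and section 8.3 adds nothing on the point. Section 4.3 further sets the objective of comparing concentrations in older and younger HIV-positive participants.

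**The concern.** After absorption, a plasma level falls until the next dose, so a single level reflects both the patient's exposure and the time at which the sample was taken. Section 6.2 allows that time to vary widely and points to a model to deal with it. The methods in 8.2 take the level as it stands.

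Three analyses under Aim 2 are exposed:

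- **Threshold comparison.** If a minimally effective concentration must be held throughout the interval, the level to test is the one at the end of it. An earlier sample can lie above the threshold in a patient who later falls below it.
- **Group comparisons.** If the usual sampling time differs between groups, that difference can appear as an effect of age. The historical database is the clearest case, because nothing in the documents says that its samples were timed as the study's are. A Mann-Whitney test takes no covariate for time.
- **Failure model.** Unadjusted variation in sampling time adds noise to the exposure variable and would tend to weaken its association with failure.

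**Working it through.** The plan gives no misclassification figure, so there is none to reproduce. It also gives no half-life, threshold value, distribution of sampling times, between-patient variability or rate of under-exposure. The inputs below are therefore assumptions, apart from the 5-hour lower limit (section 6.2).

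**Model.** First-order decline after absorption, with half-life h, dosing interval τ and sampling time t after dose:

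sampled level ÷ end-of-interval level = 2^((τ − t)/h)

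For a sample at 5 hours:

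| Half-life | τ = 24 h: 2^(19/h) | τ = 12 h: 2^(7/h) |
|---|---|---|
| 6 h | 8.98 | 2.24 |
| 12 h | 3.00 | 1.50 |
| 30 h | 1.55 | 1.18 |
| 50 h | 1.30 | 1.10 |

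**Share missed.** End-of-interval level ÷ threshold is taken as log-normal, with s = √ln(1 + CV²). A patient is under-exposed if this ratio is below 1, and is missed if the sampled level is nevertheless at or above the threshold. With true under-exposure u and all samples at one time t:

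share missed = 1 − Φ(z_u − ln 2 × (τ − t)/(h × s)) ÷ u

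Example: τ = 24, t = 5, h = 30, CV = 100%, u = 20%.

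- s = √ln 2 = 0.833.
- The shift is 0.693 × 19/(30 × 0.833) = 0.527.
- Φ(−0.842 − 0.527) = 0.0855.
- Share missed = 1 − 0.0855/0.20 = 57%.

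For spread-out sampling times the same quantity was simulated with 1,000,000 draws. Ranges cover CV 50% to 100% and true under-exposure 5% to 20%:

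| Dosing and sampling window | h = 6 h | h = 12 h | h = 30 h | h = 50 h |
|---|---|---|---|---|
| 24 h, all at 5 h | 100% | 92–100% | 57–90% | 38–72% |
| 24 h, uniform 5–24 h | 79–91% | 60–82% | 31–58% | 20–42% |
| 24 h, uniform 18–24 h | 45–71% | 26–50% | 11–26% | 7–16% |
| 12 h, uniform 5–12 h | 50–76% | 29–55% | 13–29% | 8–19% |
| 12 h, uniform 8–12 h | 33–60% | 18–39% | 7–18% | 5–11% |

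For samples within the interval the error always goes the same way, but its size runs from about 5% to about 100%.

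**Samples after the interval.** Section 6.2 sets no upper limit, so a late or missed dose can put a sample beyond τ. At 4 hours beyond, with h = 10, the ratio is 2^(−4/10) = 0.76. The sampled level is then below the end-of-interval level, and under-exposure is over-counted.

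**Group comparison.** For two groups with identical exposure and an assumed 4-hour difference in usual sampling time, the false ratio is 2^(4/10) = 1.32 at a half-life of 10 h and 2^(4/15) = 1.20 at 15 h.

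**The case against.** The best defence is that 8.2 is brief rather than wrong. Section 6.2 records the times and names sparse-data modelling as a purpose. Section 8.2 offers Mann-Whitney only as an example, leaves its list of confounders open, and foresees multivariable work. A time-adjusted analysis may well be intended. That stands as a reason not to say that the plan rules out modelling. It does not close the gap, because the methods that are stated, followed as written, mix sampling time with exposure.

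A reader might infer that most under-exposed patients will be classed as adequately exposed. The documents do not support this. They define no adequate or inadequate class, and they lack every input needed for the claim. It also fails in plausible cases. With a CV of 60% and 15% truly below the threshold, uniform sampling at 5–24 h of once-daily dosing detects 63% of the under-exposed at a half-life of 40 h. Twice-daily dosing sampled at 5–12 h detects about 51% at a half-life of 10 h.

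A reader might also infer that many samples will fall before 5 hours, in patients who dose in the morning and then attend clinic. Section 5.2 says only that "The baseline visit is expected to take 1-2 hours; if possible the subject should attend fasted". It gives no time of day for dosing or for the visit.

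Two further objections stand. Both HIV-positive cohorts follow the same sampling procedure, so a timing difference is less of a worry between them than against the historical database. And the distortion is not independent of age: it depends on half-life, and section 3.2 says that renal function declines with age and may impair elimination. A remedy that imposes one half-life on everyone could therefore bias the age comparison.

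**Conclusion.** The concern holds in a limited form. The methods stated in 8.2 do not account for time after dose, although 6.2 leaves that time open, records it and anticipates a model for it. If a minimally effective concentration is a level to be held to the end of the interval (an assumption, since the documents do not define it), samples drawn earlier under-count under-exposure and samples drawn later over-count it. The size cannot be fixed from the documents: it depends on half-life, dosing interval, sampling times and variability, all of which had to be assumed, as was first-order decline. The false ratios of 1.32 and 1.20 illustrate what a 4-hour imbalance would do; nothing shows that such an imbalance will occur. The change should be made before the pharmacokinetic analysis, because it improves on the stated method using data already planned for collection.

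**What to change.** Revise 8.2 to use the recorded dose, frequency, time of last dose and sampling time:

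- **Threshold comparison.** State what the minimally effective concentration represents. Compare it with end-of-interval concentrations predicted, within drug and regimen, by the sparse-data model that 6.2 anticipates. Add a sensitivity analysis limited to samples near the end of the interval, with that window defined in advance.
- **Group comparisons and failure model.** Adjust for time after dose within drug and regimen, or use the model-based exposure estimate. Keep raw concentrations as description, which the objective in 4.3 calls for.
- **Unusable timings.** Exclude samples drawn under 5 hours after dose, or without a recorded dose time, from these time-dependent analyses, and report how many.

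The cost is SAP wording and modelling work, with no new data from participants. Some samples are lost, and the estimates depend on the model. With one sample per visit, individual predictions shrink towards the population mean, which can itself under-count the lower tail. The model must also let elimination vary with age or renal function. The near-end-of-interval sensitivity analysis gives a partial check on both problems.
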